#### **5.5.2 Dispensing the study treatment**

Patients will receive active LFG316 or Coiporateconfidentialinformation according to their assigned treatment. LFG316 will be administered in the clinic according to the injection manual. Dispensing of Corporate Confidential Information

#### **5.5.3 Supply, storage and tracking of study treatment**

LFG316 must be received at the study site by a designated person, handled and stored safely and properly, and kept in a secured location to which only the Investigator and designated staff have access. Upon receipt, the study drugs should be stored according to the instructions specified on the drug labels.

Storage conditions must be adequately monitored and appropriate temperature/humidity logs maintained as source data. LFG316 solutions should be stored in a refrigerator at 2 to 8°C.

LFG316 Solution for Injections should be **administered immediately and should not be used after 4 hours of initial opening at room temperature.**

Any waste material (such as syringes and needles) should be disposed of in accordance with local requirements. The Investigator must maintain an accurate record of the shipment, expiration date, and dispensing of study drug in a drug accountability ledger. Drug accountability will be noted by the Monitor during site visits and/or at the completion of the trial.

The following investigation site-provided products should be stored according to the manufacturers' package inserts:

- ProparacaineHCl 0.5%ophthalmic solution
- Lidocaine2% solution
- Povidone-iodine5% solution
- Approved ophthalmic topical fluoroquinolone

To the extent possible, same batches/lots of the above mentioned investigation site-provided products should be used in the cmTent study. Batch numbers and/or lot numbers should also be recorded in a dtug accountability ledger. *Note: site standard of care may require use of other products than those listed above-in this case the same requirements for storage and accountability apply.*

All dmg supplies are to be used only for this protocol and not for any other purpose. Unless specifically instructed by Novaitis, the Investigator must not destr·oy any dtug labels, or any pa1tly used or unused dt11g supply.

At the conclusion of the study, and during the course of the study, the Investigator will provide a copy of the dtug accountability ledgerto the Monitor.

Only after receiving a written authorization by Novalits, the Investigator/designee will send all the unused and pa1tly used dtug supplies as well as the empty containers to the address provided at the time of authorization for destruction.

#### **5.5.4 Instructions for prescribing and taking of study treatment**

Please refer to the manual provided separately, for detailed instru ction on the use of LFG316. Procedures and required material related to IVT injection and preparation ai·e detailed in a separate manual.

For the usage of each vial of LFG316 the study personnel should record in the somce document the time when the solution is withdrawn in to the injection syringe.

For each patient the total dose injected (in mg), volume injected and the injection time need to be recorded in the somce document and on the Dosage Administr·ation Record eCRF page.

LFG316 may be prepared by qualified site personnel but the inu-avitreal injection must be administered by a qualifiedophthalmologist

#### **5.5.5 Permitted dose adjustment**

No dose adjustment is pe1mitted.

## 5.5.6      **Rescue**

### 5.5.6.1    **Rescue of study eye**

For any patients who meet the following criteria in the study eye, the study mug will be discontinued, and conventional therapy instituted:

- Loss of >10 letters in best corrected visual acuity (BCVA) at any visit, as compared to baseline that in the opinion of the investigator is due to worsening of uveitis.
- Active vitritis, anterior chamber inflammation, or chorioretinitis 28 ± 3 days after their last dose that, in the opinion of the investigator, is significantly worse as compared to the previous visit and requires alternate therapy
- Unilateral flare in fellow / non-study eye which does not respond to local treatment (including ozurdex® implant) or bilateral flare in both eyes which require the intensification of systemic immunosuppressive therapy.

Patients who are rescued will be asked to attend the per protocol visit schedule for the remainder of the trial in order to be followed up for safety.

Corporate Confidential Information

### 5.5.6.2    **Rescue of fellow eye**

The investigator will care for the fellow eye at his or her discretion. There are no restrictions on topical, periocular, or intravitreal therapy in the fellow eye other than those noted in [Section 5.5.7; Table 5-1](#).

NOTE: If during the trial, a patient requires systemic immunosuppressive therapy for the fellow eye, investigational therapy for the study eye should be stopped and conventional therapy instituted. The patient should continue in the study for assessment purposes. Patients who require systemic immunosuppressive therapy may be replaced to maintain adequate study power if the treatment was implemented for the sole purpose of treating the fellow eye.

### 5.5.6.3 Recommended treatment of adverse events

Ocular adverse events should be treated according to the type of adverse event. For clinically significant acute elevation of intraocular pressure (IOP) following LFG316 injection, anterior chamber paracentesis should be performed and normalization of IOP verified. For sub-acute or persistent elevation in IOP, aqueous suppressants may be indicated. Iritis or vitritis should be treated in accordance with permitted medications (see below). Endophthalmitis should be treated with vitreous paracentesis and culture and/or vitrectomy, as indicated, plus appropriate IVT antibiotics per local practice.

**NOTE:** In case of an adverse event attributed to IVT LFG316, the investigator may wish to remove the LFG316 by pars plana vitrectomy.

With any biologic treatment, systemic hypersensitivity reactions are theoretically possible. These can manifest with itching, flushing, headache, nausea/vomiting, hypotension, urticaria, bronchospasm, or angioedema. Assess and treat for anaphylaxis if indicated, and initiate supportive care. Fluids, vasopressors, corticosteroids, antihistamines, bronchodilators, and oxygen should be on hand.

Patients may remain in the study even after receiving treatment for adverse events.

Medication used to treat AEs must be recorded on the Concomitant medications/Significant non-drug therapies eCRF page after the start of study drug.

### 5.5.7 Concomitant, permitted, and prohibited treatments

Permitted and concomitant therapies are listed in [Table 5-1](#). Concomitant therapies should be entered on the appropriate CRF.

**Table 5-1 Permitted and concomitant therapies** Corporate Confidential Information

Arm:	LFG316 treatment arm	
Eye:	Study eye	Fellow eye
Complement inhibitor (other than LFG316)	Prohibited	Prohibited
Antibody (other than LFG316)	Prohibited	Prohibited
Intraocular surgery	Prohibited	Prohibited
Ocular laser	Prohibited	Prohibited
Systemic steroid or IMT already in use at screening	Permitted up to baseline Will be titrated / stopped per protocol May not be increased in dose or frequency	
New systemic steroids or IMT	Prohibited	
Intravitreal medication (other than LFG316)	Prohibited	Permitted
Periocular/intravitreal steroids	Prohibited	Permitted
New topical steroid or anti-inflammatory	Prohibited	Permitted
Cycloplegic or IOP-lowering eyedrops	Permitted	Permitted
Topical/local anesthetics and antibiotics used for intravitreal administration	Permitted	Permitted
Incidental medications not prohibited above	Permitted	Permitted

IMT = Immuno-Modulatory Therapy

### 5.5.8 Prohibited treatment

Prohibited treatments are listed above in [Table 5-1](#). If a patient is deemed to require a prohibited treatment, he or she should be withdrawn from the study.

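### Section 5.5.8 withdraws from the study patients whom Sections 5.5.6 and 6 keep on visits; read literally, it ends 1 to 6 of 7 post-dose visits, mainly a loss of safety follow-up

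*Protocol*

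**What the plan says.** Section 5.5.8 of the protocol has one rule for prohibited treatment: "If a patient is deemed to require a prohibited treatment, he or she should be withdrawn from the study". The glossary defines premature withdrawal as leaving the study, so this means more than stopping drug.

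Table 5-1 (Section 5.5.7), of which only the LFG316 arm is visible, lists "New systemic steroids or IMT" as prohibited. It also bars intraocular surgery and, in the study eye, other intravitreal medication, periocular steroids and new topical steroids.

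Four other places keep overlapping patients in the study:

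- Section 5.5.6.1, study-eye rescue: "Patients who are rescued will be asked to attend the per protocol visit schedule for the remainder of the trial". The stated purpose is safety follow-up.
- Section 5.5.6.2, systemic therapy needed for the fellow eye: "The patient should continue in the study for assessment purposes".
- Section 5.5.6.3, adverse-event treatment: "Patients may remain in the study even after receiving treatment for adverse events". For endophthalmitis the recommended treatment includes "vitrectomy, as indicated, plus appropriate IVT antibiotics per local practice".
- Section 6: patients who stop LFG316 before Day 85 are to attend every remaining visit.

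Two further passages leave the question open. Section 3.2 requires discontinuation of patients who worsen or lose vision, without saying whether from drug or from study. The withdrawal list in Section 5.5.10 is expressly not exhaustive.

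**The concern.** The treatments that trigger 5.5.8 include those the protocol itself directs. Rescue means conventional therapy, which Section 1.1 describes as local and systemic corticosteroids with or without immunomodulators. A patient whose fellow eye needs systemic therapy is told to continue by 5.5.6.2 and to leave by 5.5.8, for the same event. Section 11 permits no authorized deviations, so a site that obeys one instruction departs from the other.

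The patients concerned have worsened, or have needed eye surgery or intravitreal antibiotics. They are the ones whose later eye examinations matter most for safety. If sites resolve the conflict differently, the length of follow-up after rescue will depend on the site.

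**Working it through.** **Inputs.** Post-dose visits are on Days 2, 8, 15, 29, 43, 57 and 85 (Section 2.2). That is 7, which reproduces the count in Section 3.1; SAP Section 2.2 says 6, but the day list gives 7. Doses are on Days 1, 29 and 57. Section 7.2 requires all SAEs to be reported until 30 days after the later of last dose and last visit.

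**Earliest exit.** The criterion of losing more than 10 letters applies at any visit (5.5.6.1), so exit is possible from Day 2. The inflammation criterion applies 28 ± 3 days after a dose: 1 + 28 = 29, 29 + 28 = 57, 57 + 28 = 85.

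**Formulas.** Visits lost = scheduled days later than the exit day. Days lost = 85 − exit day. End of all-causality SAE reporting = exit day + 30, against 85 + 30 = 115 for a patient followed to Day 85. Days are nominal.

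| Exit at | Visits lost of 7 | Days lost | SAE reporting ends |
|---|---|---|---|
| Day 2 | 6 (86%) | 83 | Day 32 |
| Day 8 | 5 (71%) | 77 | Day 38 |
| Day 15 | 4 (57%) | 70 | Day 45 |
| Day 29 | 3 (43%) | 56 | Day 59 |
| Day 43 | 2 (29%) | 42 | Day 73 |
| Day 57 | 1 (14%) | 28 | Day 87 |
| Day 85 | 0 | 0 | Day 115 |

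Exits from Day 2 to Day 57 therefore lose 1 to 6 visits. Under the inflammation criterion alone (Days 29, 57 and 85) the losses are 3, 1 and 0.

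**Offset.** Section 6.3 requires Study Completion evaluations at any premature withdrawal. If that examination is counted in place of one lost visit, the net loss for exits from Day 2 to Day 57 is 0 to 5. It brings the final examination forward; it does not show the eye at Day 85.

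**What remains after exit.** Existing adverse events are followed to resolution or until judged permanent (Section 7.1). Follow-up reports on existing SAEs, and reports of new SAEs suspected to be drug-related, continue without the 30-day limit (Section 7.2). What is lost is the planned ocular examinations and reporting of new SAEs with no suspected causal link after the dates above.

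**Effect on efficacy.** SAP Section 5 includes patients in Efficacy 1, the set of primary interest, only up to discontinuation or rescue. Efficacy 2 excludes prohibited-medication use (code M01, Table 5-2). Later visits from rescued patients therefore add little to either analysis. A patient treated for an adverse event without rescue could still lose a usable Day 85 value, but this route looks narrow. At the 0.09% endophthalmitis incidence in Section 3.5, taken as per injection, 16 patients × 3 doses = 48 injections give 48 × 0.0009 = 0.04 expected cases. Vitrectomy for other adverse events is not counted there.

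**The case against.** The best answer is that the specific rule governs the general one. Four passages agree that the patient stays on visits, and one generic sentence disagrees. Table 5-1 can be read as restricting therapy given alongside LFG316, whereas rescue is a separate pathway in which LFG316 is stopped first. Section 3.1 likewise moves patients who need systemic therapy to conventional therapy. A site managing a rescue would probably consult the rescue section. This reading is sensible, but no visible text states it, and 5.5.6.2 and 5.5.8 are worded with equal force.

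Redaction also limits the point. Confidential text follows the follow-up sentences in 5.5.6.1 and Section 6 and could hold an exception. None is marked in 5.5.6.2 or 5.5.8.

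For adverse events the overlap is narrower than it first appears: "Iritis or vitritis should be treated in accordance with permitted medications". It is mainly vitrectomy and intravitreal antibiotics.

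A reader might infer three stronger things. The first is that 5.5.8 biases the primary response rate; the SAP cut-offs above mean the lost visits would mostly not have been used. The second is that withdrawn patients disappear from safety monitoring; Sections 6.3, 7.1 and 7.2 show otherwise. The third is that withdrawal lets study-eye failures be replaced by new patients. Section 4 allows replacement for non-safety discontinuations and Section 5.5.1 allows it for anyone who discontinues early. But Section 5.5.6.2 is narrower: patients given systemic therapy "may be replaced to maintain adequate study power if the treatment was implemented for the sole purpose of treating the fellow eye". Section 4's own example is also fellow-eye rescue. Replacement of failures is a possibility left open by loose wording, not something the documents plan.

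**Conclusion.** The contradiction is real and should be corrected. The loss per affected patient is the 1 to 6 visits tabulated, before crediting the exit evaluation. It assumes that 5.5.8 is applied at the visit where the prohibited treatment is first needed and that no redacted text exempts rescue. The consequence is mainly shorter safety follow-up in patients who have done badly, with little change to the planned efficacy analyses. The documents give no rescue rate, so the total effect on the trial is unknown.

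**What to change.** Reword Section 5.5.8 so that a patient who needs a prohibited treatment stops study drug and continues all scheduled visits to Day 85, unless consent is withdrawn or another withdrawal criterion in Section 5.5.10 applies. In Section 3.2, specify that patients who worsen are discontinued from study drug.

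As a secondary tidy-up, align the replacement wording in Sections 4 and 5.5.1 with 5.5.6.2, so that patients rescued for the study eye are not replaced.

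The cost is amendment text. The visits are already scheduled, and Sections 5.5.6.1 and 6 already ask these patients to attend them.

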### 5.5.9 Tapering schedule for oral corticosteroids

If a patient is receiving oral corticosteroids, one of the following schedules will be used for tapering the dose. The selection of the reduction schedule will be based on the prednisone dose the patient was receiving during the week prior to baseline.

1. For patients on up to 100 mg of prednisone-equivalent during the week prior to Day 1, the corticosteroid dose should be tapered according to the following scheme (with the exact doses determined by rounding to the nearest 5 mg): week 1, 85% of the baseline dose; week 2, 67%; week 3, 50%; week 4, 33%; week 5, 17%; week 6, 8%; weeks 7, 0%. Examples of tapering schemes in [Table 5-2](#) are provided for baseline prednisone doses in the range 10 to 100 mg/day. During this schedule, when the patient's prednisone equivalent is 20 mg/day or below, the dose should be taken in the morning after waking up to reduce suppression of the pituitary and adrenal glands.
2. For patients who previously had uveitis that was controlled with a systemic immunosuppressive drug or regimen that was discontinued and whose uveitis has flared and in whom the resumption of prednisone is not considered the appropriate systemic immunosuppressive therapy by the investigator, no prednisone will be given.

**Table 5-2 Prednisone tapering schedule (100 to 10 mg/day prior to Day 1 of study)**

Dose (mg/day) prior to Day 1	100	90	80	70	60	50	40	30	20	15	10
Week	Approx. % of baseline	Actual Daily Doses (mg)									
1	83%	85	75	65	60	50	40	35	25	15	15
2	67 %	65	60	50	45	40	35	25	20	15	10
3	50%	50	45	40	35	30	25	20	15	10	5
4	33%	30	30	25	20	20	15	15	10	5	5
5	17%	20	15	10	10	10	5	5	5	0	0
6	8%	10	5	5	5	5	5	0	0	0	0
7	0%	0	0	0	0	0	0	0	0	0	0

The oral prednisone dose may be tapered more rapidly than specified by the appropriate schedule above in the following situations:

- the patient's uveitis is subsiding rapidly and the investigator feels it is safe to accelerate the reduction in prednisone or prednisolone dose or
- the investigator feels the prednisone or prednisolone must be tapered more rapidly because of corticosteroid-related side effects.

If a patient's uveitis is not, in the investigator's opinion, improving rapidly enough to safely continue the steroid taper, the investigator may maintain the steroid dose for 1-2 additional weeks, after which the patient will resume tapering as per the weekly schedules above. This is not considered a rescue.

### 5.5.10 Discontinuation of study treatment and premature subject withdrawal

#### Study stopping criteria

If any of the following criteria is met, study enrollment and drug administration will stop:

- Two or more incidents of Serious Adverse Events that are, in the opinion of the investigator, related to LFG316 treatment *and not to the injection procedure*.
- The aggregate frequency, severity, and/or drug relatedness of adverse events merit such.
- The Sponsor requests it.

If drug administration is stopped, subjects already enrolled may remain in the study for observation only.

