## **Corporate Confidential Information**

## Patient Safety

Safety assessments will include ocular evaluations, adverse events, and serious adverse events. Cumulative safety listings will be reviewed by the Principal Investigator and the Novartis Medical Director periodically during the study, and *ad hoc* when necessary.

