were due to a common skin pathogen (*staph. Epidennidis*). Overall, these events are most likely associated with the injection procedure and not a specific chug-related toxicity. To monitor patients for these and other unexpected adverse events a comprehensive panel of ocular safety assessments based on the Phase I and Phase II studies with LFG31 6 as well as that for other of intravitreal medications will be conducted on all patients emolled. The study also includes systemic safety assessments (serum chemistries, hematology, and electrocardiogram) at Screening and end-of-study to fmther profile any systemic changes that could be associated with the patient's disease or trntment with LFG316.

All IVT injections cany a risk of endophthalmitis, retinal detachment, vitreous or retinal hemonhage, cataract, elevated intraocular pressure, and ocular inflammation. LFG316 itself could cause, in theo1y, adverse effects such as increased risk of endophthalmitis, cataract, elevated intraocular pressure, ocular inflanunation, and retinal toxicity. Patients with NIU are at inherent risk for some of these complications. LFG316 could cause existing NIU to worsen. Each of the above outcomes would be apparent on eye exam, and most would cause symptoms that would prompt the patient to seek evaluation.

As with any antibody, LFG3 1 6 may cany the risk of hypersensitiivty and patients should be monitored and managed per local center practice. LFG316 may elicit immunogenicity and the fonnation of anti-LFG316 antibodies; this has not been detected in any LFG316 trials to date.

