## Corporate Confidential Information

## **7      Safety monitoring**

### **7.1      Adverse events**

An adverse event is the appearance or worsening of any undesirable sign, symptom, or medical condition occurring after starting the study drug even if the event is not considered to be related to study drug. Study drug includes the investigational drug under evaluation and the comparator drug or placebo that is given during any phase of the study. Medical conditions/diseases present before starting study drug are only considered adverse events if they worsen after starting study drug. Abnormal laboratory values or test results constitute adverse events only if they induce clinical signs or symptoms, or are considered clinically significant, or require therapy.

The occurrence of adverse events should be sought by non-directive questioning of the subject at each visit during the study. Adverse events also may be detected when they are volunteered by the subject during or between visits or through physical examination, laboratory test, or

other assessments. All adverse events must be recorded on the Adverse Events eCRF with the following information:

1. the severity grade (mild, moderate, or severe)
2. its relationship to the study drug(s) (suspected/not suspected)
3. its duration (start and end dates or if continuing at final exam)
4. whether it constitutes a serious adverse event (SAE)

An SAE is defined as an event which:

- is fatal or life-threatening
- results in persistent or significant disability/incapacity
- constitutes a congenital anomaly/birth defect
- requires inpatient hospitalization or prolongation of existing hospitalization, unless hospitalization is for:
  - routine treatment or monitoring of the studied indication, not associated with any deterioration in condition
  - elective or pre-planned treatment for a pre-existing condition that is unrelated to the indication under study and has not worsened since the start of study drug
  - treatment on an emergency outpatient basis for an event not fulfilling any of the definitions of a SAE given above and not resulting in hospital admission
  - social reasons and respite care in the absence of any deterioration in the patient's general condition
- is medically significant, i.e., defined as an event that jeopardizes the patient or may require medical or surgical intervention to prevent one of the outcomes listed above

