## 7.2 Serious adverse event reporting

To ensure subject safety, every SAE, regardless of suspected causality, occurring after the subject has provided informed consent and until 30 days after the subject has stopped study participation (defined as time of last dose of study drug taken or last visit whichever is later) must be reported to Novartis within 24 hours of learning of its occurrence.

Any SAEs experienced after this 30-day period should only be reported to Novartis if the investigator suspects a causal relationship to the study drug. Recurrent episodes, complications, or progression of the initial SAE must be reported as follow-up to the original episode, regardless of when the event occurs. This report must be submitted within 24 hours of the investigator receiving the follow-up information. An SAE that is considered completely unrelated to a previously reported one should be reported separately as a new event.

Information about all SAEs is collected and recorded on the Serious Adverse Event Report Form. The investigator must assess the relationship of any SAE to study drug, complete the SAE Report Form in English, and send the completed, signed form by fax within 24 hours to the local Novartis Drug Safety and Epidemiology Department. The telephone and telecopy number of the contact persons in the local department of Clinical Safety and Epidemiology, specific to the site, are listed in the investigator folder provided to each site. The original copy of the SAE Report Form and the fax confirmation sheet must be kept with the case report form documentation at the study site.

Follow-up information is sent to the same person to whom the original SAE Report Form was sent, using a new SAE Report Form stating that this is a follow-up to the previously reported SAE and giving the date of the original report. The follow-up information should describe whether the event has resolved or continues, if and how it was treated, whether the drug was broken or not, and whether the subject continued or withdrew from study participation.

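### Read literally, the only numeric stopping criterion does not count a serious adverse event attributed to both LFG316 and the injection

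*Protocol*

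**What the plan says.** Protocol Section 5.5.10 lists three criteria, any one of which stops enrollment and dosing.

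- Criterion 1 is "Two or more incidents of Serious Adverse Events that are, in the opinion of the investigator, related to LFG316 treatment", immediately qualified by "and not to the injection procedure". The qualifier is set in italics.
- Criterion 2 is "The aggregate frequency, severity, and/or drug relatedness of adverse events merit such". It has no threshold.
- Criterion 3 is a request by the sponsor.

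Section 3.5 says that every intravitreal injection carries "a risk of endophthalmitis, retinal detachment, vitreous or retinal" hemorrhage, cataract, raised intraocular pressure and ocular inflammation. It then says that LFG316 itself could in theory cause "adverse effects such as increased risk of endophthalmitis, cataract, elevated intraocular pressure", ocular inflammation and retinal toxicity.

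On oversight, Section 7.2 requires reporting to the sponsor within 24 hours of "every SAE, regardless of suspected causality, occurring after the subject has provided informed consent". The synopsis, under Patient Safety, says "Cumulative safety listings will be reviewed by the Principal Investigator and the Novartis Medical Director periodically during the study", and ad hoc when needed. Section 7.4 marks a data monitoring committee as not applicable.

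**The concern.** Criterion 1 is the only stopping rule with a number in it, and with no monitoring committee it is the one rule meant to work without a further judgement on whether the safety picture justifies a stop. It joins two conditions: related to the drug, and not related to the procedure. An SAE with both causes meets the first and fails the second.

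This matters because the drug is delivered by the procedure. Section 3.5 describes how local immunosuppression could make the eye more prone to infection. An infection introduced by the needle and made worse by the drug would naturally be attributed to both. It would also be one of the drug effects the protocol says it is watching for. In a multicenter study, two investigators holding the same view of such a case could count it differently toward a mandatory stop, because the wording does not tell them what to do with a mixed cause.

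**Working it through.** The documents give no operating characteristic for the stopping rule, so there is no figure to reproduce. The check is a reading of the text, followed by one illustration of the cost.

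**Step 1. How each attribution is counted under criterion 1.**

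| Investigator's attribution | Literal reading | 'Drug rather than procedure' reading | Reworded (see fix) |
|---|---|---|---|
| LFG316 only | counts | counts | counts |
| Procedure only | does not count | does not count | does not count |
| Both | does not count | not stated | counts |
| Neither | does not count | does not count | does not count |

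Only the third row is in dispute. No section of the protocol or SAP fills it in.

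**Step 2. Is the third row foreseeable?** From Section 3.5:

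- Injection risks: endophthalmitis, retinal detachment, vitreous or retinal hemorrhage, cataract, raised intraocular pressure, ocular inflammation.
- Theoretical LFG316 effects: endophthalmitis, cataract, raised intraocular pressure, ocular inflammation, retinal toxicity.
- On both lists: endophthalmitis, cataract, raised intraocular pressure, ocular inflammation. That is four of the five theoretical drug effects.

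The overlap shows that mixed attribution can arise. It does not show how often.

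**Step 3. What counting mixed cases could cost, for the one event with a rate.**

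Inputs:
- LFG316 arm, 16 patients, with doses on Days 1, 29 and 57 (synopsis): 16 × 3 = 48 main-period injections.
- Background endophthalmitis rate, 0.03% to 0.13% per injection (Section 3.5).

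Assumptions: injections are independent, LFG316 adds no risk, and every case is an SAE judged to have both causes. Any stop that results is then unneeded.

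Formula: Pr(2 or more) = 1 − (1 − p)^48 − 48p(1 − p)^47.

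- p = 0.0003: 1 − 0.98570 − 0.01420 = 0.00010, or 0.01%.
- p = 0.0013: 1 − 0.93947 − 0.05870 = 0.00183, or 0.18%.

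This is an illustration, not a ceiling. One mixed endophthalmitis case plus one drug-only SAE, or plus one mixed SAE of another kind, would also newly meet the reworded criterion. Extension doses for responders and doses to replacement patients add injections beyond 48, and the documents do not say how many. No rates are given for cataract, raised pressure or inflammation.

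**The case against.** The strongest objection is that the ordinary reading is drug rather than procedure, and that the protocol attributes events this way elsewhere. Section 3.5 puts past events down to the procedure instead of a specific drug toxicity, and the summary of study CLFG316A2203 Part A does the same. That reading is possible. Its purpose, to keep routine injection complications from halting a drug study, is sound and should be kept. But it gives no instruction for an event with both causes, and an investigator made to choose one cause may choose the procedure.

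The second objection is that other routes cover the gap. Criterion 2 is equally binding once met and takes in frequency, severity and drug relatedness together. The sponsor can stop at any time (also Section 5.5.12.1) and sees every SAE within 24 hours. This stands, and it is why the point is small. These routes rely on judgement, however, and do not replace a numeric trigger.

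The third objection is that any rule resting on investigator opinion will vary between investigators. That is true, and rewording will not remove it. It removes only the added uncertainty about how to count an opinion already formed.

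Some stronger readings should be resisted:

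- A reader might infer that mixed-cause SAEs cannot stop the study. Criteria 2 and 3 show that they can.
- A reader might infer from Section 7.1, which asks for "its relationship to the study drug(s) (suspected/not suspected") and does not mention the procedure, that procedural attribution is not collected. The AE and SAE forms are not in the documents, so this cannot be concluded.
- A reader might want a probability that criterion 1 misses a true signal. That needs the share of drug-related SAEs judged to have both causes, and nothing in the documents supports a value.
- A reader might apply the 2 endophthalmitis cases in 153 patients to the 16 patients here. Section 3.5 says 90 of those 153 had monthly injections for up to 18 months, so the per-patient rate does not carry over to three doses.

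**Conclusion.** The wording gap is real, and the point is minor. On the literal reading, SAEs attributed to both LFG316 and the injection are left out of the only numeric stopping trigger. On the more lenient reading, their handling is undefined. SAEs attributed to the procedure alone are rightly outside the criterion and are not at issue.

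The conclusion rests on the text of Section 5.5.10, on the overlap of the two lists in Section 3.5, and on the assumption that investigators will sometimes name both causes. How often they would do so is unknown, so no size can be put on the loss of sensitivity. The point does not affect the endpoints or the analysis, and it does not show that patients are unprotected.

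**What to change.** Reword criterion 1 in Section 5.5.10, for example: *Two or more SAEs suspected to be related to LFG316, whether or not the injection procedure also contributed; SAEs attributed to the procedure alone do not count.*

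This changes one phrase, keeps the exclusion of purely procedural events, and adds no visits or assessments. The price is a slightly higher chance of an unneeded stop. For two endophthalmitis cases in the main period that chance is small, as shown in the working. For the other shared events it cannot be calculated from the documents.
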